# **Study Protocol**

# **Study Design:**

The study is a parallel community-based 2-arm randomized controlled trial (RCT) in which the study evaluations will take place at the Center of Neurorehabilitation (CNR) at Sargent College, Boston University. We will enroll 44 community-dwelling adults ages 40-80 yrs with idiopathic PD of mild to moderate disease severity, who are independent community ambulators. We will exclude those with atypical PD, have significant freezing of gait, have history of falls in the past 3 months, have a comfortable walking speed <0.4 m/s, and significant cognitive or hearing impairments. Eligible participants will be randomly allocated to either

[figure not shown]

Figure 1 Study flow. Abbreviations: CoV: Coefficient of Variation; SAM: Step Activity Monitor; SRHI: Self-Report of Habit Index

Amped-PD (experimental arm) or Active Control (control arm). Assessments will include a standard set of motor and non- motor assessments and will be administered at Baseline, Post-Assessment (after 6 weeks of training), and Follow-up (after 2 additional weeks of unstructured training). Figure 1 summarizes the study flow for the protocol.

# **Study Procedures**

# **Primary Screen (approximately 10 minutes):**

A primary screen will be conducted over the phone to make a preliminary determination if potential participants meet the initial inclusion / exclusion criteria prior to scheduling a more in-depth, in-person screening assessment. During the phone screen (see Appendix I: Primary Screen), potential participants will be asked their age (exclude if < 40 years of age), if they are currently participating in physical therapy (exclude if yes), if they are currently performing walking exercise of at least 30 min for > 3x/week (exclude if yes), and if a medical doctor diagnosed them with Parkinson disease (exclude if no). Potential participants will be asked about their ability to walk independently without physical assistance or an assistive device (exclude if no), their history of falls of > 1 fall over the past 3 months, or a singular fall over the past 3 months that is PD-related, with a fall defined as an unexpected event that caused a person to unintentionally land on a lower surface (e.g. floor, ground), regardless of presence or absence of resultant injury (exclude if yes), and whether they experience freezing episodes during daily walking (exclude if moderately or significantly disturbing – see operational definition under exclusion criteria). Lastly, a brief medical history based on self-reports from the participant will be reviewed to determine the following:

- Those with known cardiac problems that interfere with the ability to safely exercise (e.g., congestive heart failure, uncontrolled cardiac arrhythmias, chest pain) will be excluded.
- Those with known orthopedic conditions in the lower extremities or spine that may limit walking distance (e.g., severe arthritis, spinal stenosis, significant pain) will be excluded.
- Those with other medical conditions that would preclude successful participation, as determined by a physical therapist on the research team, will be excluded. The physical therapist will make this determination based on participant self-report and a PTs informed questioning which is part of a licensed PTs training.

It is possible to have self-reports of cardiac, orthopedic, or other medical conditions that may need further clarification and clinical assessment due to limited information from the participant or unclear description. The physical therapist will decide whether an in-person screening will be appropriate. Additionally, communication with the participant's physician may take place to understand their health status. A HIPAA authorization from the participant will be obtained prior to any communication with the participant's health provider.

If the participant is deemed eligible based on primary screen, the participant will be

asked about scheduling an informed consent. The participant will be given the option to receive this virtually or in-person. Virtual consenting may be administered right after the primary phone screen if the participant wishes, or may be scheduled at a different time. In-person consenting will be held on the same day of the first inclinic visit prior to any study procedure. The researcher will coordinate scheduling with the participant.

Data on the screening form will be entered into REDCap to allow investigators to monitor the number of persons screened and pass/failure rate. Potential participants who are deemed eligible based on the preliminary phone screen will be scheduled for an in-person screening and baseline assessment visit at Boston University.

# 1. First Evaluation Visit: In-Person Screening & Baseline Assessment Visit (approximately 2-3 hours):

The in-person screening and baseline assessment visit will take place at the Center for Neurorehabilitation at Boston University. All participants will have completed and provided their informed consent prior to Screening and Baseline Assessment (see Appendix II: Informed Consent; see section K). After consenting, participants will be asked to sign a HIPAA Authorization to Disclose Protected Health Information for Research Purposes (see Appendix III: HIPAA Authorization). This will allow our team to communicate directly with the participant's healthcare provider during the study if needed.

**1.aIn-Person Screening**: An in-person Screening will be administered to determine if participants meet all study inclusion/exclusion criteria. The elements included in the screening process are part of routine physical therapy evaluation. A physical exam will be conducted to assess cognitive status, Parkinson's symptoms and walking capacity.

- 1. A diagnosis of Parkinson disease will be confirmed per participant report.
- 2. The Mini-Mental State Exam (MMSE) will be administered to screen for significant cognitive impairment (exclude MMSE score < 24) (see Appendix VI: Screening Tools). The MMSE is a brief screening tool that examines cognitive impairment. Participants are tested on 11 items that cover multiple cognitive domains. The score ranges from 0-30, with higher scores indicating less cognitive impairment.

- Disease severity will be assessed by a licensed physical therapist using the Modified
- 4. Hoehn & Yahr Scale (only H&Y 1-3 will be included) (see Appendix VI: Screening Tools). The Modified H&Y Scale includes additional criteria to rate Parkinson disease symptoms on a scale from 1 to 5. Higher scores indicate increased disease progression.
- 5. Walking capacity assessments instrumented with wearable sensors:
  - The following tests on walking will be instrumented with in-lab movement sensors (XSENS, Enschede, the Netherlands), which will be worn on both mid-shank (2) and mid-thigh (2) areas, and on mid-

line low-back area (1), and the sensors of the music-based device (MedRhythms, Portland, ME), which will be secured on to the outer sides of the shoes (2). The other components of the music-based device such as its audio-cue mechanism and headphones will not be used during this screening procedure.

- The 10-meter walk test (10MWT) will be administered by a licensed physical therapist (comfortable walking speed <0.4 m/s excluded based on the average of 3 trials at comfortable walking speed) (see Appendix VI: Screening Tools). The 10MWT is an assessment of gait speed over a short distance (2 meters ramp up, 6 meters walking, 2 meters ramp down). The aforementioned distances will be pre-measured for accuracy and only the middle 6 meters will be timed. Participants will be asked to walk at a comfortable pace for 2 trials and a fast pace for 2 trials. The physical therapist conducting the test will be guarding the participant as necessary to optimize safety.

- The six-minute walk test (6MWT) (see Appendix VI: Screening Tools) will be administered by a physical therapist. The 6MWT, a measure of long- distance walking capacity, assesses how far a person can walk over a 6- minute period. The test will be performed along a pre-measured (30-meter), level, obstacle-free hallway. Participants will be instructed to walk as far as possible in 6-minutes. The physical therapist conducting the test will be guarding the participant as necessary to optimize safety. Physiological measurements (e.g., heart rate, blood pressure) and perceived ratings of walking intensity (using Borg's Rating of Perceived Exertion) will be taken prior to initiation of the walking test to determine whether the participant is safe to participate in the walking program. The participant will be excluded based on the following: resting heart rate >100 beats/min; resting systolic BP >160 mmHg, resting diastolic BP >100 mmHg. The same physiological measurements will be taken upon completion of the walking test to assess hemodynamic response to exercise.
- Walking duration from both 10MWT and 6MWT will be used to generally gauge the participant's walking tolerance. Exclude if the physical therapist determines that the participant is unable to walk independently for at least 10 minutes.
- While wearable sensors are used during the 10MWT and 6MWT, sensor data will not be used for determination of participant eligibility. Instead, sensor data will be used as part of Baseline Assessment and is integrated in this screening procedure in the clinical screening to reduce the repetition of testing of the same test (10MWT, 6MWT) during the Baseline Assessment, once the participant determined to be eligible to proceed.
- 6. Based on clinical expertise and judgement, the physical therapist conducting the in- person screening will determine if a participant requires additional guarding and/or assistance during walking activities (i.e., occasional hand contact to maintain balance or dynamic stability and/or an assistive device). If guarding is needed at any point during the evaluation,

the participant will be excluded.

- **1.b Baseline Assessment:** Participants who are deemed eligible through the inperson screen will continue on to complete the remainder of the baseline assessment measures, including:
  - Demographic questionnaire consisting of age, gender, education level, living situation, employment, ethnicity, race, and PD-specific questions. This form will be completed interview-style by the physical therapist.
  - Medication form pertaining to PD and non-PD medications (see Appendix VII: Outcome Measures). Participants will be asked during the phone screen to bring their medication list to this first evaluation visit. The physical therapist will transcribe the medications onto the designated form. Medication lists that contain identifiable information will be given back to the participant and not be kept by the research team.
  - Motor & Functional Measures:
  - Dynamic balance will be measured using the Mini Balance Evaluation Systems Test (Mini BESTest). This test comprises of 14 items that span anticipatory postural adjustments, reactive postural control, sensory orientation, and dynamic gait.
  - ii. Motor symptoms will be assessed using the Movement Disorder Society Unified Parkinson Disease Rating Scale (MDS-UPDRS)-III (see Appendix VII: Outcome Measures). The MDS UPDRS is the most widely used clinical rating scale fork Parkinson disease. Part III is a motor examination (33 scores summed from 18 questions) conducted by the rater. Total scores can range from 0 to 141, with higher scores indicating worse disease severity.
  - iii. Quantification of movement will be performed using in-lab movement sensors (XSENS, Enschede, the Netherlands) and sensors of the music-based device (MedRhythms, Portland, ME) (see Appendix VII: Schematic of Wearable Sensors). These sensors will be used to measure gait quality during performance of the 10MWT and 6MWT as performed in the inperson screening, and to measure posture as examined in posture-related items within the UPDRS III and Mini BESTest. Sample metrics include but are not limited to gait velocity, stride length, cadence, and limb velocities, and postural sway measures based on velocity, magnitude, smoothness. As a clarification, the instrumented 10MWT and 6MWT as performed during the initial screen provide the data needed for this Baseline Assessment, therefore these tests will not be repeated.
  - iv. Functional Mobility will be measured via the Five Times Sit to Stand (5xSTS). The 5xSTS objectively assesses the time it takes to complete 5 sit-to-stands and is a method to observe movement strategies or compensations. The test will be performed in a standard chair with participants instructed to stand up and sit down 5 times as quickly as possible. The physical therapist conducting the test will be guarding the participant as necessary to optimize safety; however, if guarding is needed for the 5xSTS, participants will not be allowed to continue with the

intervention.

- Self-report/ Interview Measures:
  - i. Section I and II of the Movement Disorder Society Unified Parkinson Disease Rating Scale (MDS-UPDRS) will be utilized to assess non-motor and motor signs. Section IA includes 6 items related to non-motor experiences such as cognition, mood, and motivation which are assessed by the examiner. Section IB consists of 7 items related to non-motor aspects of experiences of daily living such as sleep and fatigue which are filled out by the participant (with or without the help of a caregiver), but independent of the examiner. Section II is a self-administered questionnaire consisting of 13 items related to motor aspects of experiences of daily living.
  - ii. The Self-Report Habit Index (SRHI) will be administered to measure exercise-habit strength and automaticity. This self-report index comprises of 12 statements with constructs spanning behavior repetition, automaticity, and identity, with responses made on 11-point Likert scales (0 = strongly disagree; 10 = strongly agree) (see Appendix VII: Outcome Measures).
- iii. Self-Efficacy of Walking Duration (SEW-D) is a 10-item self-report that will be administered to determine participants' beliefs of their physical capabilities to successfully complete incremental 5-minute intervals (5 to 40 minutes) of walking at a moderately fast pace, with responses made on 11-point Likert scale (0% = not at all confident; 100% = highly confident).
- iv. Geriatric Depression Scale (GDS) is a brief, self-report involving yes/no questions instrument on psychological aspects and social consequences of depression in the elderly. The short form of GDS of 15-items will be used in this study.
- v. Health-related quality of life will be measured by the Parkinson's Disease Questionnaire 39 (PDQ-39)(see Appendix VII: Outcome Measures). The PDQ-39 is a self-report questionnaire that assesses quality of life over the past month across 8 different dimensions. Items are scored based on a 5-point ordinal system with lower scores reflecting better quality of life.
- Walking Activity:
  - Step Activity Monitor: Walking activity will be measured using the StepWatch 4 Activity Monitor (SAM; Orthocare Innovations, Mountlake Terrace, Washington). The SAM is a self-contained, maintenance-free device that combines acceleration, position and timing information to count complete gait cycles (strides) of the user. It is the size of a pager, weighs 38g (roughly the weight of two AA batteries for comparison) and will be attached with self- adhesive straps above the lateral malleolus (where the shin meets the foot) of the participants' less impaired lower extremity. Data from the SAM, which includes measurement of daily step counts and step intensities, will allow us to examine changes in physical activity in response to the intervention. The validity and reliability of the SAM for capturing stride counts has been demonstrated in persons with various neurological disorders including PD (Shepard 1999, Coleman

- 1999, Macko 2002, Salarian 2004, Gaines 2005, Manns 2009, Speelman 2011).
- General wear instructions and considerations: Participants will be instructed to wear the SAM for 4-11consecutive days depending on the assessment timepoint. The SAM will be worn continuously during all waking hours, expect when bathing, showering, or swimming. The physical therapist will fill out the SAM researcher form to appropriately document the SAM calibration process for each participant. Participants will be given instructions on how to don/doff the device and will be provided with a form to record times the SAM is removed over wear period. The SAM requires no maintenance by the user besides remembering to keep it on. The physical therapist will provide strategies to help the participant remember to put the SAM back on if they do take it off at any time (e.g., if the SAM is taken off at night, place it on a nightstand next to the bed so it is seen in the morning).
- Specific wear schedule for Baseline Assessment: For the Baseline Assessment, the SAM will be worn for 4 consecutive days prior to initiating the intervention (and will continue to wear it for another 7 days during training please see next section 2. Intervention). Participants will be contacted via phone within 24-48 hours following the evaluation session to ensure that they are comfortable with the device and to address any questions or concerns. Furthermore, participants will be notified that they may contact study staff during work hours at any point during the wear period if they experience any technical issues with the SAM or have any questions.
- Operation and data download: Using the manufacturer's software, the SAM will be calibrated by a physical therapist to each participant's gait pattern based on height, typical walking speed, and leg motion. Collected data will be downloaded to a tablet computer, with which manufacturer's software will convert stride counts to step counts and calculate daily step count values. No identifiable information is collected by the SAM.
- 1.cRandomization: At the completion of procedures for Baseline Assessment, the participant will be randomized to receive either the experimental or control arm of the intervention. The experimental arm, called Amped-PD, is a 6-week community-based structured walking program that uses a music-adaptive RAS followed by 2 weeks of unstructured walking protocol (continue as desired) for a total of 8 weeks. The control arm, called Active-Control is a similarly structured 6-week community-based walking program that does not use RAS, followed by 2 weeks of unstructured walking protocol (continue as desired) for a total of 8 weeks of training. Block randomization with balanced allocation between the two groups will be implemented. A randomization list will be generated prior to enrollment of participants. The researcher will gain knowledge of treatment assignment only after procedures in In- person Screen and Baseline Assessments have been completed.

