# 1.d Device Training Amped-PD Intervention:

# Training Procedures / Instruction to Participants:

# Music-Based Device Training (Only for Amped-PD)

Participants who are randomized to receive Amped-PD intervention will undergo training on how to use how to use the music-based device and independently conduct the remote walking program. The music-based device (MedRhythms, Portland, ME) is specifically designed for gait training in people with neuromotor impairments. Participants will be trained to independently use the device. A simple setup which takes < 2 min involves initiating the smartphone application, wearing the headphones, and attaching a movement sensor to the outer side of each shoe below the ankle. The smartphone is kept in the user's pocket throughout the session. The music-based device obtains real-time walking information through the shoe sensors that communicate wirelessly with the smartphone application software. The music-based device delivers music cues that are adjusted according to the user's walking pace as detected by the shoe sensors. These music cues serve as the substrate for rhythmic auditory stimulation during walking.

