Training with the music-based device will be administered after completing the In-person screening and Baseline Assessment procedures. To ensure that the participant is able to hear the music, the physical therapist will have the participant put on the headphones while music is played. The physical therapist will instruct participants to listen to the music at a safe volume so they can still hear sounds in their environment. The participant will then practice donning/doffing, adjusting the volume, setting up, and using the device (i.e., walk for 5 minutes) to demonstrate comprehension and independent use. A team member will provide the participant with the necessary equipment (i.e., smartphone, shoe sensors, headphones, study diary). The physical therapist will be able to determine safe and independent walking ability during the 5 minutes of walking with the device. Five minutes is enough time for the participant to experience an increase in music tempo and for the physical therapist to determine if guarding is needed during these transitions. At the end of this training period, if the physical therapist determines that the participant will need continued assistance from another person to walk and perform transitions (i.e. turns, step initiation) while using the music-based device, the participant will be withdrawn from the study. Otherwise, the physical therapist will proceed and discuss the space and location in which the participant plans to conduct the walking program, and review space adequacy and safety considerations. A safe environment will be considered to be the following: indoor spaces - level surfaces, obstacle-free, no slippery surfaces, no unsecure area rugs; outdoor spaces – avoid auto or bike traffic, obstructive tree roots, divots in the asphalt and concrete. These environments could include, but are not limited to: home, apartment building hallway, neighborhood sidewalks, local track or park, office environments, and community/ recreation centers. Ideally the space is at least 50 feet in length that meet the above indoor and outdoor space criteria. This will decrease

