#### 2. Intervention:

# Amped-PD: Remote Walking Program Description

(prescribed walking program of 15 hours total over six weeks + concurrent use of SAM device 4 days during early training)

**Overview:** The remote walking program is a self-directed, structured walking program held in home/community settings using the music-based device. Participants will be instructed to complete five home/community-based walking sessions per week (one session/ day, 30 minutes in duration) for six weeks. Participants may choose to perform these 5 training sessions on any days of the week according to their needs.

**Description of Walking Program:** Using the music-based device, participants will conduct the walking sessions at their self-selected pace in

a home/community environment that limits the amount of stops and/or pivot turns in order to optimize continuous walking. For the purposes of this study, home/community environment is considered any environment outside a professional healthcare facility. This includes but is not limited to the home, apartment building, independent living retirement homes, outdoor environments (tracks, parks, sidewalks), office environments and community/ recreation centers.

**Duration of Walking Session:** Each individual walking session will be completed within a 30- minute timespan (i.e., should not be split up throughout the day). Participants are allowed to rest as needed during the 30-minute training period. The time clock will continue to run down continuously once the 30 minutes are started (i.e., if a participant rests for 5 minutes, this will equate to 25 minutes of walking). Participants will be instructed to terminate any walking session in the event of technical or medical issues to allow for adequate resolution.

**Walking program diary:** Participants will be asked to record in a study diary their schedule (dates and times) of walking, location, record of any falls they experience and any comments/issues they experience while using the device (see Appendix VII: Outcome Measures).

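### Do the conflicting step-monitor wear lengths and the unwritten timing of allocation undermine the baseline for daily steps and moderate-intensity minutes?

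*Protocol*

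**What the plan says.** Protocol section 1.b (Walking Activity) gives the monitor's role: "Data from the SAM, which includes measurement of daily step counts and step intensities, will allow us to examine changes in physical activity". The SAP lists moderate-intensity minutes and daily steps among four primary outcomes and compares the arms on change from baseline at 6 and 8 weeks.

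On the baseline window, section 1.b says: "For the Baseline Assessment, the SAM will be worn for 4 consecutive days prior to initiating the intervention". It then adds 7 further days once training starts. The Step Activity Monitoring paragraph of section 2 repeats the 7 days and gives a total of 11 days of unbroken wear. The Active-Control section adopts that paragraph by cross-reference. The bracketed line under the title of each arm's walking program instead reads: "concurrent use of SAM device 4 days during early training".

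On the order of events, section 1.c says: "At the completion of procedures for Baseline Assessment, the participant will be randomized". It adds: "The researcher will gain knowledge of treatment assignment only after procedures", where the procedures meant are the in-person screen and the baseline assessments. Section 1.d says: "Training with the music-based device will be administered after completing the In-person screening and Baseline Assessment procedures". The contact described after the first visit and before training is a call: "Participants will be contacted via phone within 24-48 hours following the evaluation session".

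**The concern.** The length conflict is a plain contradiction in current text. The Active-Control section even disagrees with itself: its heading gives 4 days, while its cross-reference brings in 7.

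The order matters more. If wear is unbroken from baseline into training, no day is left between the two for allocation and for the Amped-PD device session. That session needs the participant and the therapist in the same place. The call at 24 to 48 hours is a check on comfort with the monitor and cannot replace it, and the next numbered visit is the Post-Assessment.

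If allocation in fact happens at the first visit, participants would know their arm while the so-called baseline steps are being counted. Participants handed a music device might walk more, or controls might hold back. Any such difference between arms would pass straight into the change scores for two primary outcomes.

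**Working it through.** **Inputs.** Baseline wear of 4 days (sections 1.b and 2). Training wear of 7 days (sections 1.b and 2, running text) or 4 days (headings of both arms). Total of 11 days (section 2). General wear range of 4 to 11 days (section 1.b). Five 30-minute sessions a week on days the participant chooses (section 2). Change at 6 and 8 weeks from baseline (SAP).

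**1. Reproduce the stated total.** 4 + 7 = 11, which matches section 2 and the top of the 4-to-11 range. The headings give 4 + 4 = 8, which matches no stated total. The running text is therefore consistent with itself in three places, and the headings stand apart. The 4 baseline days are the same on either count.

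**2. Which analysis uses the disputed days?** Let B be the baseline value, E the early-training value, and Y6 and Y8 the later values. The between-group tests compare Y6 − B and Y8 − B. E is in neither. At most E enters the within-group repeated-measures analysis, whose timepoints the SAP does not list. This covers the opening run only. A similar 7-against-4 difference between section 3 and the heading of section 4 concerns follow-up wear and is not judged here.

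**3. How far would E depend on the window?** There are C(7,5) = 21 ways to place 5 session days in a week. The number with k sessions in the first 4 days is C(4,k) × C(3,5−k):

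- k = 2: 6 × 1 = 6 patterns, 2 × 30 / 4 = 15 min/day
- k = 3: 4 × 3 = 12 patterns, 3 × 30 / 4 = 22.5 min/day
- k = 4: 1 × 3 = 3 patterns, 4 × 30 / 4 = 30 min/day

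A 7-day window always gives 5 × 30 / 7 = 21.4 prescribed min/day. If the window opens on the day of the first session, 15 patterns remain (3, 9 and 3 for k = 2, 3 and 4). If these are equally likely, their mean is (3×2 + 9×3 + 3×4) / 15 = 3.0 sessions, or 22.5 min/day. The average gap between the two windows is then 22.5 − 21.4 = about 1 min/day. An individual's value can differ by more, but none of it reaches the between-group tests.

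**4. Order of events.** Set side by side, section 1.b makes the 4 SAM days part of the Baseline Assessment, section 1.c randomises once its procedures are complete, and section 1.d puts device training after them. Read literally, that gives SAM days, then allocation, then device training, then the first session. It is a sound order, and it also limits disclosure: staff who do not yet know the arm cannot tell the participant.

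**5. Effect on the contrast.** Let r_A and r_C be the average reactions that enter B in the two arms. The between-group difference in change shifts by −(r_A − r_C). Under the literal order neither reaction can depend on the arm, so the expected shift is 0. A reaction common to both arms also cancels. Only a reaction that differs between arms, after early disclosure, would bias the result. The documents give no figure from which to size that.

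**The case for a change.** The strongest case is that sections 1.c and 1.d are numbered under the First Evaluation Visit, which is an in-person contact at which both could be done. Since no later attendance is described before training, a site could well allocate and train at that visit and send the participant home with the monitor. The baseline days would then follow allocation in a comparison where participants know whether they have the device. The SAP does not say which SAM days form the baseline.

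Part of this stands. The readable text does not name the contact, and the first-visit reading cannot be ruled out. But that reading works only if SAM wear is not a baseline procedure, and section 1.b says it is. It also answers the complaint that there is no contact at which these steps could occur, so the two halves of the concern do not hold together. Figure 1 shows the study flow and has SAM in its abbreviation list. Because it is missing from the text available here, the absence of a written contact cannot be counted against the plan.

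The SAP's silence on which days count is filled by section 1.b, which already limits the baseline to days before training. The monitor yields daily counts and the diary records session dates, so an analyst can separate the two periods.

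**Conclusion.** No change to the plan follows. The 7-or-4 conflict is a clerical slip between headings and running text. It leaves the 4-day baseline and the between-group 6- and 8-week change scores untouched, and at most bears on an early-training value that the SAP never names. It can be tidied whenever the protocol is next edited.

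The timing of allocation is a missing detail, not a flaw in the design. The stated order puts the baseline days first, with zero expected bias. Rewording would choose neither an order nor a length, and a sentence defining the baseline days would largely repeat section 1.b. A reported count of pre-allocation days or an optional sensitivity analysis would leave the primary analysis as it is.

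This rests on three assumptions: the literal order is the one followed; the SAM is the source of moderate-intensity minutes, which is inferred from its recording of step intensity; and Figure 1 does not contradict the text. If the baseline days in fact followed disclosure of the arm, the bias would be of unknown size and direction, and would arise only from a reaction that differed between arms.
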